20.3.2 Benefit Assessment

Preliminary anti-tumour activity has been observed with AZD4573 as monotherapy in participants with r/r haematological malignancies in the ongoing Phase I, FTIH, dose-escalation study (D8230C00001; see Section 2.2.6). [CCI](#)

Clinical benefit in patients with MCL has been reported for other CDK inhibitors. In a Phase II study of MCL participants receiving flavopiridol, PR occurred in 11% (95% CI, 2%-28%) of participants and the median duration of response was 3.3 months (range 2.8-13.2) ([Kouroukis et al 2003](#)). In a Phase I study among 16 participants with lymphoma receiving dinaciclib, one participant had MCL; this participant had an 8% reduction in tumour mass ([Baiocchi et al 2010](#)).

The addition of agents which in combination could provide more continuous anti-tumour activity may reasonably be expected to significantly enhance clinical benefit with manageable changes to risk. Acalabrutinib, a BTK inhibitor like ibrutinib, has been shown to inhibit proliferation and induce apoptosis in B-cell malignancies ([Davis et al 2010](#), [Harrington et al 2016](#)). The latter is likely due to the ability of BTK inhibitors to increase certain pro-apoptotic BCL2 family proteins, like Bim, ([Deng 2017a](#), [Deng et al 2017b](#), [Sasi et al 2019](#)) pushing the cancer cells closer to their apoptotic threshold, a mechanism known as ‘apoptotic priming’ ([NCCN 2021](#), [Ni Chonghaile et al 2011](#)). Capitalising on this apoptotic priming, addition of AZD4573 following a short lead-in of acalabrutinib in the OCI-LY10 DLBCL xenograft model causes an increase in both the magnitude and duration of anti-tumour response, compared to either monotherapy, as demonstrated by more rapid and robust cleavage of caspase-3 and delayed time to tumour regrowth following treatment cessation (Patent WO2019/058348; data on file, AstraZeneca). Acalabrutinib is a highly selective,

potent, covalent inhibitor of BTK with minimal off-target activity leading to a safety profile that may be attractive for combination strategies.

20.3.3 Overall Benefit/Risk Conclusion

Eligible participants will be r/r to prior treatments for their disease, have received one prior line of therapy, and for whom a clinical study is the best option (in the opinion of the Investigator) for next treatment based on response and/or tolerability to prior lines of therapy. Furthermore, participants will have varying levels of disease burden at study entry and almost certainly have acquired mutations as part of their disease course. Therefore, there is no guarantee that any participant will derive clinical benefit during this study.

AstraZeneca believes the anticipated benefits that may be afforded to participants with r/r haematological malignancies currently outweigh the identified and potential risks associated with AZD4573 in combination with acalabrutinib.

As described, the study design aims to minimise risks and build on the preliminary efficacy seen to date in the ongoing FTIH study (D8230C00001), reflecting clinical responses in a r/r participant population. Thus, the benefit/risk assessment for administration of AZD4573 with acalabrutinib is considered acceptable for participants with r/r MCL.

For an assessment of benefit and risks pertaining to the conduct of this study during the COVID-19 pandemic, refer to Appendix [A 11](#).

21 OBJECTIVES AND ENDPOINTS – MODULE 2

Objectives and Endpoints for Part A are outlined in [Table 26](#). An additional primary objective was included for Module 2, regarding AZD4573 monotherapy in MCL.

Table 26 Objectives and Endpoints – Module 2

Objectives	Endpoints
Primary	
Part A	

Assess the safety and tolerability of the RP2D of AZD4573 in combination with acalabrutinib (100 mg BID) for participants who are administered AZD4573 monotherapyAssess the safety and tolerability and confirm the RP2D of AZD4573 monotherapy in MCL	
Adverse events (including SAEs), dose modifications, treatment discontinuation due to AE, AESIs, laboratory data, vital signs, and ECG changesAdverse events (including SAEs), dose modifications, treatment discontinuation due to AE, AESIs, laboratory data, vital signs, and ECG changes
Secondary	
Part A	

Assess the plasma PK of AZD4573 (when given alone and in combination with acalabrutinib 100 mg) and acalabrutinib (plus its active metabolite ACP-5862)	
Plasma concentrations and derived PK parameters for AZD4573 for the PK analysis setPlasma concentrations and derived PK parameters for acalabrutinib and its metabolite ACP-5862 for the PK analysis set

Objectives	Endpoints
Exploratory	
Part A	

 Explore activity of AZD4573 alone, and in combination with acalabrutinib by evaluation of tumour responses and overall survival 	
 Endpoints based on revised response criteria for malignant lymphoma (Cheson et al 2014): 
 ORR Proportion of participants with CR DoR TTR PFS OS

 Assess the PD of AZD4573 (alone and in combination with acalabrutinib) and the PD of acalabrutinib (in combination with AZD4573) 	
 CCl [REDACTED]

 CCl [REDACTED] 	
 CCl [REDACTED]

 CCl [REDACTED] 	
 CCl [REDACTED]

Abbreviations: AE = adverse event; AESI = adverse event of special interest; BID = twice daily; CR = complete response; CCl [REDACTED] ECG = electrocardiogram; MCL = mantle cell lymphoma; CCl [REDACTED] PK = pharmacokinetics; CCl [REDACTED] RP2D = recommended Phase II dose; SAE = serious adverse event; CCl [REDACTED]

The study design of Part B of this module will be determined from the data emerging from Part A. Specifics for Part B will be defined in a future protocol amendment.

22 STUDY DESIGN – MODULE 2

Module 2 will not open for enrolment until the RP2D for AZD4573 + acalabrutinib has been established in Part A of Module 1.

22.1 Overall Design

Module 2 is a window study comprising 2 cycles (8 weeks) of AZD4573 monotherapy (Period 1) followed by AZD4573 + acalabrutinib combination treatment (Period 2). It will enrol participants with r/r MCL who have failed at least one line of prior therapy, are not eligible for curative treatment options. AZD4573 will be administered in Part A as monotherapy (Period 1) and in combination with acalabrutinib 100 mg twice daily (Period 2). Cycle 1 of each dosing period has a duration of 35 days; subsequent cycles have a duration of 21 days. AZD4573 should be administered at least 5 days apart.

The AZD4573 monotherapy RP2D includes an intra-patient ramp up; participants will receive AZD4573 6 mg at Cycle 1 Week 1, AZD4573 9 mg at Cycle 1 Week 2, and AZD4573 12 mg from Week 3 and thereafter.

The AZD4573 FTIH study (Study D8230C00001) established the AZD4573 monotherapy RP2D in DLBCL (12 mg once weekly), but the dose setting did not include any MCL participants. Hence, in Part A, Period 1 of Module 2 aims to confirm the AZD4573 monotherapy RP2D in MCL participants. If AZD4573 monotherapy is not tolerated in r/r MCL participants, there will be no dose exploration/dose setting conducted in this study. At this time, it is unlikely that AZD4573 monotherapy would be developed at a dose lower than 12 mg in MCL.

Participants will move from AZD4573 monotherapy to combination treatment (AZD4573 + acalabrutinib) based on the Lugano overall response ([Cheson et al 2014](#)). See [Table 36](#) for details.

In Period 2, the safety and tolerability of the RP2D of AZD4573 + acalabrutinib established in Module 1 will be assessed in participants with MCL. As participants will have reached an AZD4573 dose of 12 mg 1QW (the maximum dose in combination with acalabrutinib in dose setting Module 1) during Period 1, a further intra-patient ramp up will not be required in Period 2 Cycle 1. Treatment with AZD4573 + acalabrutinib combination therapy may be continued until disease progression, an unacceptable drug-related toxicity occurs, or the participant withdraws or is withdrawn from the study as defined in the protocol.

The SRC will meet after the first 6 participants have completed Part A, Period 1, Cycle 1, and again after the first 6 participants entering Period 2 have completed Cycle 1. The SRC will

continue to monitor safety and tolerability data for all participants in Part A. For further details refer to Section [27.5](#).

The data cut-off for the primary analysis of Part A will occur approximately 6 months following last-participant first-dose of AZD4573 monotherapy or when 75% of participants have progressed or died in Part A, whichever occurs first. All available data from Period 1 (AZD4573 monotherapy) and Period 2 (AZD4573 plus acalabrutinib) will be analysed.

Additional data cuts may also be performed.

All participants will be followed for survival until death, loss to follow-up, the Sponsor closes the study, or withdrawal of consent, whichever occurs first.

The study design of Part B of Module 2 will be determined from the data emerging from Part A. Specifics of Part B will be defined in a future protocol amendment.

[figure not shown]
The final analysis will be conducted at the end of the module.

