22.2 Scientific Rationale for Study Design

The study design proposed is based on both preclinical and clinical data. Mcl-1 has been shown to be highly expressed in 2 human MCL cell lines and in tumours from 12 of 36 patients with MCL, and expression appeared to correlate with high-grade morphology ([Khoury et al 2003](#)). Aberrant expression of *MCL-1* has recently been implicated in lymphomagenesis ([Zhou et al 2001](#)), and it is hypothesised that the expression of *MCL-1* could contribute to the pathogenesis of MCL. [CCI](#) [REDACTED]

[REDACTED]

CCI

CCI

[figure not shown]
CCI

CCI

CCI

CCI

Clinical benefit in participants with MCL has also been reported for other CDK inhibitors. Partial response occurred in 11% (95% CI, 2%-28%) of participants with MCL receiving flavopiridol in a Phase II study, the median DoR was 3.3 months (range 2.8-13.2) (Kouroukis et al 2003). Among 16 participants with lymphoma receiving dinaciclib in a Phase I study, one participant had MCL and an 8% reduction in tumour mass was recorded (Baiocchi et al 2010).

Acalabrutinib, is approved by the FDA for the treatment of adults with MCL who have received at least one prior therapy. In a Phase II study of acalabrutinib involving 124 participants with r/r MCL, 81% of participants had a CR (40%) or PR (41%) after a median of 15.2 months of follow-up. Kaplan-Meier estimates of median DoR, PFS, and OS were not reached (Wang et al 2018). At long-term follow-up after a median of 38.1 months, the median DoR was 28.6 months (95% CI 17.5-39.1 months] and median PFS was 22.0 months (16.6-33.3 months) (Wang et al 2020).

The combination of AZD4573 and acalabrutinib may yield greater clinical benefit than either treatment alone. The effect of acalabrutinib in lowering the apoptotic threshold by induction of pro-apoptotic proteins or reduction of anti-apoptotic proteins (Deng 2017a) is expected to play an additive or synergistic role in targeting the apoptotic defects when administered in combination with AZD4573. CCI

As there are limited data available on AZD4573 monotherapy in patients with MCL, Part A of the Module 2 study design includes a window study of 2 cycles of AZD4573 monotherapy in each participant before starting combination treatment with acalabrutinib. This approach will allow AZD4573 monotherapy dose confirmation in participants with MCL before investigating the anti-cancer activity of the AZD4573 and acalabrutinib combination treatment.

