23.5 Justification for Dose

Part A

The ongoing FTIH study (D8230C00001) has demonstrated that administration of AZD4573 is tolerated in participants with r/r haematological malignancies. The study has established a recommended Phase II dose (RP2D) of AZD4573 monotherapy in DLBCL participants involving intra-patient dose ramp up in Cycle 1 from a starting dose on Day 1 (6 mg), with subsequent titration to the intermediate dose on Day 8 (9 mg), and to the target dose of 12 mg on Day 15, with weekly IV administration thereafter at the target dose (data on file, AstraZeneca). This established dose of AZD4573 monotherapy in DLBCL participants will be administered in Part A, Period 1 of Module 2 to participants with r/r MCL.

Acalabrutinib 100 mg BID is the approved dosage for patients with MCL ([Calquence United States Prescribing Information](#)). Module 1 of this study evaluates the safety and tolerability of AZD4573 in combination with acalabrutinib 100 mg BID in participants with DLBCL. The target dose of AZD4573 9 mg was tolerated in combination with acalabrutinib, and the target dose level of 12 mg is being explored in participants with DLBCL (data on file, AstraZeneca).

The dose of AZD4573 administered in combination with acalabrutinib during the combination Period 2 of Module 2 to participants with MCL will be established based on emerging data from Module 1 and will be a dose deemed by the SRC to be tolerated in combination with acalabrutinib in participants with DLBCL (ie, the RP2D in DLBCL).

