24.4 Duration of Therapy

Participants will move from AZD4573 monotherapy to combination treatment (AZD4573 + acalabrutinib) based on the Lugano overall response ([Table 36](#)) ([Cheson et al 2014](#)).

Table 29 **Part A - Duration of AZD4573 Monotherapy**

Disease Assessment	Lugano 2014 Overall Response	Treatment	Next Scheduled Disease Assessment
Period 1, Cycle 2, Week 3 ^a	CR	Continue AZD4573 monotherapy (Period 1, Cycle 3)	Period 1, at Cycle 5, Week 3
	PR	Continue AZD4573 monotherapy (Period 1, Cycle 3)	Period 1, at Cycle 5, Week 3
	SD	Continue AZD4573 monotherapy (Period 1, Cycle 3) ^b	Period 1, at Cycle 5, Week 3
	PD	Start combination therapy (Period 2, Cycle 1)	Period 2, after 2 cycles (Section 26.4.2)
Period 1, Cycle 5, Week 3 ^a	CR	Continue AZD4573 monotherapy (Period 1, Cycle 6)	Period 1, after 8 cycles (Section 26.4.2)
	PR	Continue AZD4573 monotherapy (Period 1, Cycle 6) ^b	Period 1, after 8 cycles (Section 26.4.2)
	SD	Start combination therapy (Period 2, Cycle 1)	Period 2, after 2 cycles (Section 26.4.2)
	PD	Start combination therapy (Period 2, Cycle 1)	Period 2, after 2 cycles (Section 26.4.2)

^a Schedule the disease assessment to ensure availability of Lugano overall response ([Cheson et al 2014](#)) before Day 1 of the subsequent cycle.

^b AZD4573 + acalabrutinib combination treatment (Period 2, Cycle 1) can be started at the discretion of the investigator.

Note: AZD4573 + acalabrutinib combination treatment (Part A, Period 2) shall be started, if the participant develops PD at any time during the AZD4573 monotherapy (Part A, Period 1).

Abbreviations: CR = complete response; PD = progressive disease; PR = partial response; SD = stable disease.

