25.2 Patient Withdrawal from the Study

Please refer to Section [7.2](#) for information on participant withdrawal from the study.

In addition for Module 2, participants who experience an AE during the dosing ramp up (Period 1 Weeks 1-3) that result in inability to complete the dosing ramp up will permanently discontinue AZD4573 and exit the study.

25.3 Procedures for Handling Participants Incorrectly Initiated on AZD4573 or Combination Therapy

Please refer to Section [7.3](#) for information on procedures for handling participants incorrectly initiated on AZD4573 or combination therapy.

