Electrolyte panel: sodium, chloride, calcium, magnesium, potassium.

If an unscheduled ECG is done at any time, then an electrolyte panel (ie, calcium, magnesium, potassium), and troponin must be done to coincide with the ECG testing.

Supra-renal glands: T4, cortisol, adrenocorticotrophic hormone (ACTH) and thyroid-stimulating hormone (TSH) should be measured at the following timepoints:

- Screening

Period 1 and Period 2

- Cycle 2, Day 1
 - Predose AZD4573 (within 72 hours prior to infusion)
- 30-Day SFU

Pancreas: Lipase and amylase measurements are required at the following timepoints:

- Screening

Period 1 and Period 2

- Cycles 1 through 8:
 - Predose AZD4573 (within 72 hours prior to infusion)

- Cycles 9+, on Day 1 of each Cycle:
 - Predose AZD4573 (within 72 hours prior to infusion)
- 30-Day SFU

Lipase/amylase tests do not need to be repeated before first dose if the first-dose visit is within 3 days of the Screening sample.

TLS monitoring will include: potassium, calcium, phosphate, uric acid, and creatinine. TLS monitoring will be performed at the following timepoints:

Period 1 and Period 2

- Cycle 1, Weeks 1 through 3
 - Predose AZD4573
 - 6 hours (\pm 30 minutes) after the start of the infusion
 - 24 hours (\pm 1 hour) after the start of the infusion (and prior to acalabrutinib dosing in Period 2)

Participants showing signs of clinical or laboratory TLS at 6 hours after the start of the infusion must be admitted for in-patient TLS monitoring for a minimum of 24 hours after the start of the infusion and monitored every 4 to 6 hours during this time (or more frequently if clinically indicated).

For each TLS monitoring timepoint, a TLS Monitoring page in the eCRF is to be filled out.

Liver chemistry tests: For any participant on study who experiences elevated ALT /AST $\geq 3 \times$ ULN and/or elevated total bilirubin $\geq 2 \times$ ULN: repeated liver chemistry tests (INR, fibrinogen, D-dimer [where available at institution], ALP, ALT, AST, GLDH, CPK, total bilirubin, direct bilirubin, indirect bilirubin) are required at 48 hours (-2/+12 hours) and 96 hours (-2/+12 hours) after the start of the infusion and until resolution of the event. However, in case the event is not resolved within 96 hours the medical monitor should be contacted. If GLDH cannot be performed locally, LDH will be analysed locally and a serum sample must be collected for central retrospective GLDH analysis. Refer to the Laboratory Manual for details.

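### Module 2: Section 26.1.7 requires TLS monitoring in Period 2 but Table 24 omits it, and the Section 22.1 ramp-up waiver assumes a 12 mg dose that a switch on early progression does not guarantee

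*Protocol*

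**What the plan says.** **Ramp-up.** AZD4573 in Period 1 is 6 mg in Week 1, 9 mg in Week 2 and 12 mg from Week 3 (Day 15). Section 22.1 drops the ramp-up in Period 2 for a stated reason: "As participants will have reached an AZD4573 dose of 12 mg 1QW (the maximum dose in combination with acalabrutinib in dose setting Module 1"). From this premise the same sentence goes on to draw its conclusion, worded as follows: "during Period 1, a further intra-patient ramp up will not be required in Period 2 Cycle 1". Section 22.2 describes the intended course: Part A "includes a window study of 2 cycles of AZD4573 monotherapy in each participant before starting combination treatment with acalabrutinib". The note to Table 29 (Section 24.4) adds that the combination "shall be started, if the participant develops PD at any time during the AZD4573 monotherapy". Section 25.2 removes from the study "participants who experience an AE during the dosing ramp up (Period 1 Weeks 1-3) that result in inability to complete the dosing ramp up"; it does not mention progression. The Period 2 dose is left to Module 1. Section 23.5 reports: "The target dose of AZD4573 9 mg was tolerated in combination with acalabrutinib, and the target dose level of 12 mg is being explored".

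**TLS monitoring.** Section 26.1.7 lists predose, 6 h and 24 h checks in Cycle 1 Weeks 1-3 under a heading that names both periods. Its 24 h entry reads "after the start of the infusion (and prior to acalabrutinib dosing in Period 2"). It continues: "Participants showing signs of clinical or laboratory TLS at 6 hours after the start of the infusion must be admitted for in-patient TLS monitoring". A TLS eCRF page is required for each timepoint. Table 23 (Period 1) has a TLS row. Table 24 (Period 2) has neither a row nor a footnote on TLS monitoring. Section 26.1.8 says that monitoring follows the Schedule of Activities. Table 23 footnote o and the TLS Prophylaxis, Monitoring, and Management text end monitoring once one target-level dose has been given, which means at least the first three weekly doses.

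**The concern.** TLS is an important identified risk for AZD4573, an identified risk for acalabrutinib, and listed in Section 20.3.1 as a potential overlapping toxicity. The 6-hour check decides whether a participant is admitted or goes home. When acalabrutinib is first added, a site working from Table 24 would not schedule that check, and a site working from Section 26.1.7 would. Safety and tolerability of the combination is a primary objective of Part A, so sites should collect the same safety data.

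The ramp-up waiver states its premise as fact. The Table 29 switch is mandatory and carries no minimum dose or time, so the premise can fail for a participant who progresses during the ramp-up. The text does not say at what dose that participant starts the combination.

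**Working it through.** No figure in the protocol needs reproducing. The check sets the texts side by side and adds simple dose arithmetic.

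**1. TLS monitoring in Period 2**

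| Place | What it implies for Period 2 |
|---|---|
| Section 26.1.7 | Required: predose, 6 h, 24 h, Cycle 1 Weeks 1-3 |
| Table 24 and footnotes a to jj | No TLS entry |
| Section 26.1.8 | Follow the schedule, so none |
| Table 23 footnote o; TLS management text | Ends after one target-level dose, at least the first 3 doses |

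An ordinary entrant switches at the 8-week assessment (35 + 21 = 56 days). By then, with no dose held, the 12 mg doses number 3 (Cycle 1 Weeks 3-5) + 3 (Cycle 2 Weeks 1-3) = 6. The stopping rule is met, which agrees with Table 24 and conflicts with Section 26.1.7.

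What Table 24 lacks, by timepoint:
- Predose: covered by clinical chemistry (footnote k).
- 24 h: covered by clinical chemistry (footnote k).
- 6 h: no laboratory counterpart. The participant is on site for vital signs at 6 h in Weeks 1-3 (footnote c).

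The chemistry panel in Section 26.1.7 contains all five TLS analytes: potassium, calcium, phosphate, uric acid and creatinine. The conflict is therefore confined to the 6-hour check and the TLS eCRF page.

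**2. Dose at an early switch**

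Inputs: ramp-up of 6, 9 and 12 mg on Days 1, 8 and 15; Period 2 dose of 9 or 12 mg (the two levels named in Section 23.5). Assumption: the switch happens before the next ramp-up dose is given.

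Ratio = first Period 2 dose / highest prior dose.

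| Doses received | Period 2 at 9 mg | Period 2 at 12 mg |
|---|---|---|
| 6 mg only | 9/6 = 1.5 | 12/6 = 2.0 |
| 6 and 9 mg | 9/9 = 1.0 | 12/9 = 1.33 |

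The planned step after 6 mg is 9 mg, and after 9 mg it is 12 mg. Only 6 mg to 12 mg skips a step, which is 1 of the 4 combinations.

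**3. The stopping rule at an early switch**

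Doses still to come of the first three: 3 - 1 = 2 after 6 mg only, and 3 - 2 = 1 after 6 and 9 mg. The stopping rule is not met in either case. For this participant Section 26.1.7 and the stopping rule both require TLS monitoring in Period 2, and only Table 24 leaves it out.

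**4. How an early switch could arise**

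The first scheduled post-baseline assessment is at 8 weeks, well after Day 15. Progression before Day 15 therefore needs an unscheduled assessment, which Section 26.4.2 allows. The documents give no rate for this, and the point does not depend on one.

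**The case against.** A reader might infer that, following the protocol as written, a participant who progresses early gets no 6-hour check. The documents do not support that. Section 26.1.7 prescribes the check, the stopping rule continues monitoring for at least the first three doses, Section 26 describes the schedule as a summary of procedures, and the Table 24 chemistry row refers to Section 26.1.7. The fault is an omission from one table. A partial reply is that Section 26 also calls adherence to the schedule essential and required, so the omission can still mislead a site.

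A reader might also infer that TLS monitoring ought to restart for every Period 2 entrant. That goes beyond the text: an ordinary entrant has met the stopping rule, and no Period 2 TLS risk figure is given that would justify overriding it.

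On the ramp-up, the other side can fairly say that the waiver gives its reason and so need not reach a participant for whom the reason fails, that saying a ramp-up is not required does not forbid one, and that progression before Day 15 should be rare. All of that stands and limits the weight of the point. It does not supply a rule for the case that the Table 29 note creates. Such a rule could sit in text not available for this review (the synopsis, core Sections 4.1, 6.12, 7.1 and 7.2, and the Figure 6 scheme).

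Other safeguards also stand: TLS prophylaxis is mandatory for all infusions, uric acid must be below the upper limit of normal before each one, and extra TLS laboratory tests are permitted when clinically indicated.

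**Conclusion.** Both inconsistencies are present in the text shown, and both are minor.

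The firmer one is TLS monitoring. Section 26.1.7 and Table 24 cannot both be right for Period 2, and the difference is one 6-hour check per week for three weeks, plus the eCRF page. The ramp-up waiver is a corner case: its premise can fail only for progression before Day 15, and a step is skipped only from 6 mg alone to 12 mg. The size of that jump assumes that the Period 2 dose is 12 mg, which Module 1 was still to settle, and that the switch comes before the 9 mg dose.

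Nothing here affects the sample size, an estimate or an error rate. Section 18.5 refers to a decision to halt enrolment permanently, so few or no participants can still be affected. The correction matters mainly for any further amendment or reuse of the window design.

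**What to change.** 1. **Section 22.1.** Make the waiver conditional: no Period 2 ramp-up for participants who have received and tolerated at least one AZD4573 dose at or above the Period 2 dose level. All others complete the remaining ramp-up steps in Period 2 Cycle 1, with TLS monitoring. Refer to this rule in the Table 29 note.
2. **Table 24 and Section 26.1.7.** Add a TLS row to Table 24 (predose, 6 h, 24 h) that applies at least to participants who have not yet met the stopping rule, and word the Period 2 requirement in Section 26.1.7 to match.
3. **Sponsor's choice, not a correction.** The row could cover all Period 2 entrants in Cycle 1 Weeks 1-3. The TLS management text would then have to say that monitoring restarts in Period 2.

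Cost: one conditional sentence, one cross-reference, one table row and a matching edit. Items 1 and 2 add nothing for participants who met the stopping rule in Period 1. Completing the ramp-up delays the full dose by at most one week, and only for someone who had 6 mg alone and would start Period 2 at 12 mg. Item 3 would add a 6-hour draw and TLS eCRF pages in three weeks. The participant is already on site at that hour, but the volume should be checked against the 350 mL expected maximum for Period 2 Cycle 1 in Section 26.
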